#### 3.3.3. Randomization

Randomization of study subjects will be done in 3:1 ratio to the treatment arm and control arm. Due to the nature of study treatment, this is an unblinded study. A randomization list will be prepared by the SCCCBiostatistics and implemented by the research staff.

After each patient's study eligibility is confirmed and the informed consent is signed, the research staff will enter the required subject information into the CIERRA system in order to register the subject. The coordinator of the PI will receive the designated patient ID, study arm, randomization number, and randomization date. Coordinator will print the randomization confirmation form from the CIERRA system and place it in the subject's research chart and then notify the requesting member of the study team of the treatment assignment for the new randomized subject.

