### 13.2 Sample Size Justification/Accrual Rate

The analysis set (evaluable subjects) consist of study-eligible subjects who either complete three treatments/three study visits and the biopsy visitor are withdrawn from the study due to showing evidence of PD during the study (non-responder). Subjects will be non-evaluable when they do not wish to continue in the study, are unable to continue in the study, or they cannot complete treatments or study visits for any reason other than PD. There will be 15 evaluable subjects in the treatment arm and 5 evaluable subjects in the control (non-treatment) arm. We expect that three to four subjects in both treatment arm and control arm will be non-evaluable. Therefore, the planned maximum number of enrolled subjects will be 28. The number of subjects is small due to the preliminary nature of the study, yet similar in size to previous studies (Konnikov et al 2011 and Shah et al 2009), which only used the 595 nm laser. Out of our 15 subjects in the treatment arm, we expect eleven or more subjects will respond to proposed treatment (either CR or PR). The table below shows significance (p-value) of hypothetical study findings assuming one BCC per subject. As shown in the second row, if one out of five subjects in the control arm shows either CR or PR and twelve or more out of fifteen subjects in the treatment arm show either CR or PR then test of comparing proportions of two arms is statistically significant (p-value < 0.05). If none in the control arm show either CR or PR and nine or more out of fifteen subjects in the treatment arm have either CR or PR, we also get a statistically significant difference indicating a better response rate in the treatment arm.

Number of subjects (CR or PR) among 15 subjects in the treatment arm vs. 5 in control arm	p-value*
11 (73.3%) vs. 1 (20%)	0.058
12 (80%) vs. 1 (20%)	0.031
9 (60%) vs 0 (0%)	0.030

\* one-sided Fisher's exact test (assuming every subject has one BCC)

One to two subjects will be accrued per week secondary to availability of the laser.

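### The 3:1 ratio, the maximum of 28, three to four losses per arm and 15 v 5 evaluable subjects cannot all hold: the expected yield is 18 v 4 or 17 v 3

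*Combined protocol and SAP*

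**What the plan says.** Section 3.3.3 fixes the allocation: "Randomization of study subjects will be done in 3:1 ratio to the treatment arm and control arm". It mentions a prepared randomization list but not whether the list is blocked.

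Section 13.2 gives the other three figures. The target is "There will be 15 evaluable subjects in the treatment arm and 5 evaluable subjects in the control (non-treatment) arm". On losses it says "We expect that three to four subjects in both treatment arm and control arm will be non-evaluable". From these it concludes: "Therefore, the planned maximum number of enrolled subjects will be 28".

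Non-evaluable subjects leave the analysis set. They include those who decline or are unable to continue, and cases where "they cannot complete treatments or study visits for any reason other than PD". All three p-values in the 13.2 table (0.058, 0.031 and 0.030) come from a one-sided Fisher's exact test under the column heading "Number of subjects (CR or PR) among 15 subjects in the treatment arm vs. 5 in control arm". The same section expects eleven or more of the 15 laser subjects to respond. It gives no power figure.

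**The concern.** The maximum of 28 appears to have been built by adding the same number of losses to each arm. Equal additions to unequal arms change the ratio, so the total no longer matches a 3:1 list. Control is the small arm, and a loss of three or four there takes a large share of it.

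At stake is the only quantitative support for the sample size. The table shows what results would be significant at 15 v 5. If the enrolment plan is not expected to deliver 15 v 5, the table describes a different trial from the one that will be run. Because the list is built from the ratio, a control shortfall found late could not be made good within the cap.

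**Working it through.** **Inputs.** Ratio 3:1 (3.3.3). From 13.2: evaluable 15 and 5, losses 3 to 4, maximum 28, expected laser response 11/15 = 73.3%, one-sided Fisher at p < 0.05. The control response rate is my assumption: 0% and 20%, the two rates in the plan's own table rows.

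**Step 1: reproduce 28.**
- Four lost per arm: (15+4) + (5+4) = 19 + 9 = 28, a ratio of 19/9 = 2.1.
- Three lost per arm: 18 + 8 = 26.
- Three to four lost in total: 20+3 = 23 or 20+4 = 24.

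Of these readings of the stated losses, only four per arm gives 28, and it is not 3:1.

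**Step 2: apply the stated ratio.** 28 × 3/4 = 21 laser and 28 × 1/4 = 7 control.
- Three lost per arm: 21−3 = 18 and 7−3 = 4.
- Four lost per arm: 21−4 = 17 and 7−4 = 3.

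The same loss counts are 3/21 to 4/21 (14% to 19%) of laser subjects but 3/7 to 4/7 (43% to 57%) of controls. Keeping 3:1 and five evaluable controls after these losses would take 8 or 9 randomized controls, so 4×8 = 32 or 4×9 = 36 enrolled, above the cap.

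**Step 3: reproduce the p-values.** For *a* responders of *n* laser subjects and none of *m* controls, p = C(n,a)/C(n+m,a). With one control responder, p = [C(n,a+1) + m·C(n,a)]/C(n+m,a+1).
- 9/15 v 0/5: 5005/167960 = 0.030.
- 12/15 v 1/5: (105 + 5×455)/77520 = 0.031.
- 11/15 v 1/5: (455 + 5×1365)/125970 = 0.058.

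All three match the plan.

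**Step 4: fewest laser responders for p < 0.05.**

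| Evaluable | No control responder | One control responder |
|---|---|---|
| 15 v 5 | 9/15 (60%), p=0.030 | 12/15 (80%), p=0.031 |
| 18 v 4 | 11/18 (61%), p=0.045 | 15/18 (83%), p=0.046 |
| 17 v 3 | 12/17 (71%), p=0.049 | 16/17 (94%), p=0.046 |

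For example, 12/17 v 0/3 is 6188/125970 = 0.049, and 16/17 v 1/3 is (1 + 3×17)/1140 = 0.046.

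**Step 5: exact power.** Sum Bin(a; n, 11/15) × Bin(b; m, p0) over all pairs (a, b) whose Fisher p is below 0.05, where p0 is the assumed control rate.

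| Evaluable | Control rate 0% | Control rate 20% |
|---|---|---|
| 15 v 5 | 92% | 48% |
| 18 v 4 | 92% | 48% |
| 17 v 3 | 71% | 38% |

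At 18 v 4 the three extra laser subjects offset the missing control. At 17 v 3 the two extra do not.

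**The case against.** Several points on the other side are fair, and they limit how far this goes.

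- A reader might infer that power falls whatever happens. It does not: at 18 v 4 it is unchanged.
- A reader might infer that the trial will certainly end with three or four controls. The losses are expectations and blocking is not stated. Under unblocked 3:1 randomization, the chance of 8 or more controls among 28 is 0.40 and of 9 or more is 0.25. Eight are needed if three are lost, and nine if four are lost. A shortfall is the expected result, not a fixed one.
- A reader might infer that the tabulated p-values are wrong. They are correct for 15 v 5, and the final Fisher test is valid at whatever sizes occur.
- Power and success thresholds are not quantities the plan commits to. The table presents hypothetical results and assumes one lesion per subject; section 13.3.2 uses another test if some subjects have more.
- This is a pilot, and 13.2 says its size is small for that reason.

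Two rescues can be tried. Losses of 6 laser and 2 control would fit 28, 3:1 and 15 v 5 exactly, but 13.2 says three to four in both arms. The firm wording of the 15 and 5 target might imply replacement until the targets are met, but a 3:1 list yields about 7 controls by the cap, and no section gives a rule for filling the control arm.

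The objections reduce the size of the effect. They do not remove the contradiction.

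**Conclusion.** The inconsistency stands: sections 3.3.3 and 13.2 state four figures that cannot all be true. On the stated ratio, cap and per-arm losses, the expected evaluable sample is 18 v 4 or 17 v 3, not 15 v 5. The ratio is met exactly only if the list is blocked with blocks complete at 28; otherwise 21:7 is an average.

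The practical effect depends on the losses. With three per arm it is negligible. With four per arm, the case from which 28 was derived, power falls by 21 percentage points (92% to 71%) at a 0% control rate and by 10 (48% to 38%) at 20%. Those figures rest on the plan's 11/15 laser rate, my assumed control rates and one lesion per subject. The plan is wrong as written on this point, but the documents do not support saying that the comparison is lost.

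**What to change.** Reconcile 3.3.3 with 13.2 before the list is issued. Keeping 3:1 and a maximum of 28, there are two ways:

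1. If three to four losses per arm is what the sponsor expects, restate the evaluable sample as 17–18 v 3–4 and recompute the p-value table for those sizes.
2. If the sponsor actually expects losses in proportion to arm size, restate them as 6 laser and 2 control (21−6 = 15, 7−2 = 5). The existing table then stands.

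Both are wording changes in 13.2 and need no extra subjects and no new allocation.

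If the sponsor instead means four losses per arm with 15 v 5 evaluable, the allocation that fits within 28 is 19:9. That changes 3.3.3 and the list, and puts two more subjects in the untreated arm than 21:7 (9−7 = 2). It is a design choice for the sponsor, not a correction that the documents dictate.

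Whichever is chosen, 3.3.3 should say whether the list is blocked, since that decides whether the split is exact or only expected.

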#### **13.3.2 Efficacy**

Each BCC will be assessed for response as specified in Section 9.0.

If all subjects have one BCC, the overall response rates (CR or PR) for treatment and control arms will be estimated by the percentage of subjects achieving these criteria and compared using one-sided Fisher's exact test. The corresponding two-sided 95% confidence intervals will be estimated by the exact binomial method.

If some study subjects have more than one BCC, response rate will be defined as the number of BCCs achieving CR or PR divided by total number of BCCs for all subjects in each arm. We will use Donner's adjusted  $\chi^2$  test with one degree of freedom to compare response rates between the treatment and control arms. The corresponding two-sided 95% confidence intervals will be estimated using Jung and Ahn's method. We also report percentage change in lesion size for both treatment and control arms.

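### At 15 v 5 the planned one-sided Fisher test is valid but needlessly conservative (type I error at most about 1.5%); Boschloo's exact test also holds 5% and gains about 7 to 22 points of power

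*Combined protocol and SAP*

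**What the plan says.** All references are to the combined protocol and SAP.

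- Section 13.2, numbers: "There will be 15 evaluable subjects in the treatment arm and 5 evaluable subjects in the control (non-treatment) arm".
- Section 13.2, expectation: "Out of our 15 subjects in the treatment arm, we expect eleven or more subjects will respond to proposed treatment". No expected control response rate is given.
- Section 13.2, table of hypothetical results, by one-sided Fisher's exact test with one BCC per subject: 11 v 1, p = 0.058; 12 v 1, p = 0.031; 9 v 0, p = 0.030. The text calls a result significant when p is below 0.05. No power is stated.
- Section 13.3.2, if all subjects have one BCC: response rates are to be "estimated by the percentage of subjects achieving these criteria and compared using one-sided Fisher's exact test", with exact binomial 95% confidence intervals for the rates. If some subjects have more than one BCC, the comparison moves to lesion level and uses Donner's adjusted chi-square test.

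**The concern.** The sponsor's table already shows that 11 of 15 laser responders against 1 of 5 controls misses 0.05. Part of the reason is the small control arm, and part is the test. Fisher's test conditions on the total number of responders. With only 5 controls, few outcomes are possible for each total, so the attained type I error sits well below the nominal level.

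What is at stake is power. The study exists to judge whether the laser merits further work (Section 13.1), and its sample is small. If another exact test keeps the same 5% guarantee and rejects in more of the plausible outcomes, the planned test gives up information that no extra subject would be needed to recover.

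**Working it through.** **Inputs.** 15 and 5 evaluable subjects, one-sided test, threshold 0.05, laser rate 11/15 = 73.3% (all Section 13.2). Control rates of 0%, 10% and 20% are assumptions: 0/5 and 1/5 are the plan's hypothetical rows, and 10% lies between them.

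**1. Reproduce the plan's p-values.** For a laser and b control responders with total t = a + b, Fisher p is the sum over k ≥ a of C(15,k)·C(5,t−k)/C(20,t).

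- 11 v 1: (1365×5 + 455)/125970 = 7280/125970 = 0.0578
- 12 v 1: (455×5 + 105)/77520 = 2380/77520 = 0.0307
- 9 v 0: 5005/167960 = 0.0298

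All three agree with the table in 13.2.

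**2. Fisher's type I error.** Over all 16 × 6 outcomes, Fisher rejects with at least 9 v 0, 12 v 1 or 14 v 2, and never with 3 or more control responders. Under a common response rate π, the rejection probability is the sum over those outcomes of C(15,a)·C(5,b)·π^(a+b)·(1−π)^(20−a−b). It peaks near π = 0.70:

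0.00243×0.8689 + 0.02835×0.2969 + 0.1323×0.0353 = 0.0021 + 0.0084 + 0.0047 = 0.0152

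In each product the first factor is the chance of 0, 1 or 2 control responders; the second is the chance of at least 9, 12 or 14 laser responders. The probability is 1.24% at π = 0.5 and 0.03% at π = 0.2.

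**3. Boschloo's test.** Its p-value is the maximum over π of the probability, under a common rate, of a Fisher p no larger than the one observed. Fisher's test is valid, so this maximum cannot exceed the Fisher p itself. Hence every Fisher rejection is also a Boschloo rejection; the enumeration found no exception.

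| Result | Fisher p | Boschloo p |
|---|---|---|
| 11 v 1 | 0.058 | 0.026 |
| 12 v 1 | 0.031 | 0.013 |
| 9 v 0 | 0.030 | 0.010 |

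| Control responders (of 5) | Fewest laser responders, Fisher | Fewest laser responders, Boschloo |
|---|---|---|
| 0 | 9 | 7 |
| 1 | 12 | 10 |
| 2 | 14 | 13 |
| 3 | none | 15 |

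Boschloo's maximum type I error is 4.75%, at π of about 0.55.

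**4. Power at a laser rate of 11/15.** Power is the sum over b of P(b control responders) × P(laser responders at or above the boundary for b). At a 20% control rate:

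- Fisher: 0.3277×0.9229 + 0.4096×0.4027 + 0.2048×0.0616 = 0.480
- Boschloo: 0.3277×0.9933 + 0.4096×0.8125 + 0.2048×0.1940 + 0.0512×0.0095 = 0.699

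| Control rate | Fisher | Boschloo | Gain (points) |
|---|---|---|---|
| 20% | 48% | 70% | 22 |
| 10% | 68% | 87% | 19 |
| 0% | 92% | 99% | 7 |

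**5. Dependence on the ordering.** For 11 v 1, an unconditional test that orders outcomes by the pooled Z statistic also gives 0.026. An unpooled Z ordering gives 0.082, so the words "exact unconditional" alone do not fix the result.

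**The case against.** - **Fisher's test is a legitimate choice.** It is valid, prespecified and familiar, and the sponsor prints 0.058 openly. This stands: nothing is miscalculated or hidden.
- **The 1.5% takes the unconditional view.** Conditional on the total number of responders, Fisher's attained level reaches 3.2% (at 14 v 2), and 3.1% and 3.0% at 12 v 1 and 9 v 0. This is a fair point in a long-standing debate. It does not remove the practical comparison: both tests keep 5% unconditionally, and Boschloo rejects everything that Fisher does.
- **The gain comes with a lower bar.** Under Boschloo, 7/15 v 0/5 (p = 0.036) and 10/15 v 1/5 (p = 0.0475) would also be significant. The study is unblinded, and a partial response can rest on a 10% decrease in lesion size measured by ruler (Sections 4.0 and 9.2). The threshold of one-sided 0.05 is already lenient; at 0.025, 11 v 1 would still miss under Boschloo (0.0263). These are real costs of reading a positive result, and they stand.
- **The fix may not apply.** Sections 4.0 and 5.1 allow subjects with several BCCs. If any such subject is in the analysis, 13.3.2 uses Donner's test and the figures above do not describe the comparison. This limit also stands.

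A reader might infer that the sponsor's own expected result fails its own test. The documents do not say so: the expectation is eleven or more laser responders with no control count attached, and 11 v 1 is one hypothetical row. A reader might also infer that a laser performing as predicted would be wrongly discarded. No go/no-go rule depends on p < 0.05, and the response rates with their intervals are reported whatever the p-value.

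**Conclusion.** The point holds as a matter of efficiency. For the one-BCC-per-subject case at 15 v 5, Fisher's test uses less than a third of its nominal 5%, and Boschloo's test recovers about 7 to 22 points of power with the same guarantee and no additional subjects. The gain passes 20 points only when the control rate is as high as 20%.

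The power figures assume a laser rate of 11/15, control rates of 0% to 20% that the plan does not itself predict, and exactly 15 and 5 evaluable subjects. Other evaluable numbers would change the figures, but Boschloo's p-value would still never exceed Fisher's.

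**What to change.** - In 13.3.2, for the case where every subject has one BCC, name one-sided Boschloo's exact test at 0.05 as the primary comparison, with its ordering (by Fisher p-value) stated in advance. Keep one-sided Fisher as a sensitivity analysis.
- In 13.2, recompute the table and state power at a laser rate of 11/15 for control rates from 0% to 20%.
- Add an exact confidence interval for the difference in response rates, since 13.3.2 plans intervals only for the rates themselves. State its method and level, because a two-sided 95% interval need not agree with a one-sided test at 0.05.
- Leave Donner's analysis for multiple BCCs as it is.

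The cost is a few sentences and a re-run table in standard software, settled before outcome data are seen. The test is less familiar to readers, and the report should say plainly that smaller differences now count as significant.

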### **13.3 Planned statistical analyses**

#### **13.3.1 Subject characteristics**

Subject demographics (age, sex, race/ethnicity) and disease characteristics (type of BCC, size of BCC, site of BCC, number of BCCs per subject, Fitzpatrick skin types, etc.) will be summarized using descriptive statistics: counts and percentages, range, median, mean, and standard deviation, as appropriate. Descriptive statistics will also be provided for size of BCC at baseline and subsequent visits and displayed as box plots for each study arm. We will also calculate percentage change in size of BCC from baseline and display in a spider plot.

#### **13.3.2 Efficacy**

Each BCC will be assessed for response as specified in Section 9.0.

If all subjects have one BCC, the overall response rates (CR or PR) for treatment and control arms will be estimated by the percentage of subjects achieving these criteria and compared using one-sided Fisher's exact test. The corresponding two-sided 95% confidence intervals will be estimated by the exact binomial method.

If some study subjects have more than one BCC, response rate will be defined as the number of BCCs achieving CR or PR divided by total number of BCCs for all subjects in each arm. We will use Donner's adjusted  $\chi^2$  test with one degree of freedom to compare response rates between the treatment and control arms. The corresponding two-sided 95% confidence intervals will be estimated using Jung and Ahn's method. We also report percentage change in lesion size for both treatment and control arms.

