## 9.0 MEASUREMENT OF EFFECT

### 9.1 Guidelines for Evaluation of Measurable Disease

We will measure disease both clinically and histologically. Clinically, a dermatologist will visually inspect for the lesion and measure the size of any residual tumor with perpendicular diameters ( $d_1$  and  $d_2$ ). Surface area (SA) will be calculated as that for an ellipse, by  $SA = \pi r_1 r_2$ , where  $r_1 = d_1/2$  and  $r_2 = d_2/2$ . Residual tumor burden will be calculated by change in surface area of the lesion. Histologically, an excisional biopsy will be performed in order to examine for any residual tumor cells in the lesion. We will classify response according to our criteria below.

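### Lesion area is measured at baseline and Day 84, but the only planned between-arm comparison is a responder cut at 90% of baseline; percentage change in area is described and never compared

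*Combined protocol and SAP*

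**What the plan says.** Section 9.1 takes two perpendicular diameters, converts them to an ellipse area, and states: "Residual tumor burden will be calculated by change in surface area of the lesion". Section 4.0 applies this at initial evaluation and Day 84 in both arms. Section 5.2 adds measurements at each visit.

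The primary endpoint is CR or PR. In the Section 9.2 table a lesion responds if it is absent or at most 90% of its baseline size, and histology only separates CR from PR. (The CR text in 9.2 sets no size limit when histology is negative, so the cut is purely at 90% only under the table.)

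Section 13.3.2 has the response rates "compared using one-sided Fisher's exact test" if every subject has one BCC, and uses Donner's adjusted chi-square test otherwise. For size it says only: "We also report percentage change in lesion size for both treatment and control arms". Section 13.3.1 is also descriptive: "Descriptive statistics will also be provided for size of BCC at baseline and subsequent visits", with box plots and a spider plot.

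On numbers, Section 13.2 says: "There will be 15 evaluable subjects in the treatment arm and 5 evaluable subjects in the control (non-treatment) arm". It also says: "Out of our 15 subjects in the treatment arm, we expect eleven or more subjects will respond". It gives p-values for three hypothetical results, but no power and no assumed control response rate.

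**The concern.** The responder cut scores an 11% shrinkage the same as full clearance, and a 9% shrinkage the same as no change. With five controls, little information is left after that cut. The graded measurement that would restore some of it is already collected but never compared between arms.

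The pilot is meant to show whether the laser merits a larger trial. Section 13.2's own table shows that the lowest laser result it expects, 11 of 15, is not significant against one control responder (p = 0.058). If the arms are compared on size only after the data are seen, in an unblinded study, that comparison will carry little weight. An interval for the size difference would also help to plan the larger trial.

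**Working it through.** **Inputs from the documents.** 15 v 5 evaluable subjects, one-sided Fisher test, p < 0.05, and expected laser response 11/15 = 73.3% (Sections 13.2 and 13.3.2). Control response appears only as hypothetical results, 1/5 or 0/5. The SD of area change and the share of cleared lesions are not given.

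**1. The plan's p-values.** With C(20,5) = 15,504 ways to choose the control arm:
- 11 v 1: [C(8,5) + 12·C(8,4)]/15,504 = (56 + 840)/15,504 = 0.058
- 12 v 1: [C(7,5) + 13·C(7,4)]/15,504 = (21 + 455)/15,504 = 0.031
- 9 v 0: C(11,5)/15,504 = 462/15,504 = 0.030

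All three reproduce.

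**2. Rejection region.** The laser arm needs at least 9 responders with 0 control responders, 12 with 1, and 14 with 2 (p = 496/15,504 = 0.032). With 3 or more control responders no result is significant (15 v 3 gives 816/15,504 = 0.053).

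**3. Power of the planned test.** Power = sum over b of P(b of 5 controls respond) × P(laser responders reach the limit for b). At a 73.3% laser rate the limits are reached with probability 0.923, 0.403 and 0.062.
- Control 20%: 0.328 × 0.923 + 0.410 × 0.403 + 0.205 × 0.062 = 0.302 + 0.165 + 0.013 = **48%**
- Control 10%: 0.590 × 0.923 + 0.328 × 0.403 + 0.073 × 0.062 = 0.545 + 0.132 + 0.005 = **68%**
- Control 5%: 0.774 × 0.923 + 0.204 × 0.403 + 0.021 × 0.062 = 0.714 + 0.082 + 0.001 = **80%**

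The actual size of the test is at most about 1.5%.

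**4. Rank test on percentage change.** Assumption: the log of (Day 84 area / baseline area) is normal in each arm, with means set so that the share at or below 0.90 equals the stated response rate. With equal SDs the arms then differ by z(0.733) + z(0.80) = 0.623 + 0.842 = 1.465 SD. Simulated one-sided 5% power at 73.3% v 20%, no lesions cleared:

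| Log-SD, control / laser | Rank test | Fisher |
|---|---|---|
| 0.3 / 0.3 | 83% | 48% |
| 0.3 / 0.6 | 79% | 48% |
| 0.15 / 0.5 | 69% | 48% |
| 0.15 / 1.0 | 58% | 48% |

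Adding cleared lesions leaves most results in this range; the most favourable case (equal SDs, 30% cleared) reached 89%. If responders in both arms shrink equally, the rank test gives 58% to 62%.

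At lower control rates the rank test gives mostly 81% to 97% (10% control) and 88% to 99% (5% control). At log-SDs of 0.15 / 1.0 it gives 65% to 66% and 70% to 72%, below Fisher's 68% and 80%.

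**5. Baseline-adjusted area models, 73.3% v 20%.** Log-area ANCOVA gives about 86% with equal SDs and no cleared lesions. With a larger laser-arm SD it gives 44% to 71%. With 30% cleared it gives 37% to 51%, and it needs an arbitrary constant because log area is undefined at zero. ANCOVA on untransformed area gave 24% to 75% in the same scenarios. Both can fall below Fisher.

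**The case against.** The strongest reply is that this is a 20-subject pilot gathering preliminary evidence, and that describing a secondary size measure is a defensible choice. Box plots, standard deviations and spider plots are already planned. Ruler measurement in an unblinded study is open to assessor influence, so a p-value could lend it more weight than it deserves. These points stand. They are why the comparison should be supportive only.

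Part of the gap is also due to Fisher's conservatism. An exact unconditional test on CR+PR has 70% power at 73.3% v 20%. Against that test the rank test gains about 13 points when shrinkage is graded, and nothing when responders in both arms shrink equally. This too stands, though neither test on CR+PR uses the degree of shrinkage.

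A reader might infer three stronger things that the documents do not support:
- **That an area analysis would have over 80% power.** This needs similar variability in both arms, and no SD is given. Section 1.1 describes growth as slow, so untreated lesions may well vary less than treated ones.
- **That the planned test is more likely to miss the effect than find it.** This holds at a 20% control rate but not at 10% or 5%, and the plan assumes no control rate.
- **That baseline is ignored, or that area is available for everyone.** Response is already defined relative to each lesion's own baseline, so most of the gain comes from not dichotomising. Subjects withdrawn for progression leave before Day 84, and three to four per arm may be non-evaluable.

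**Conclusion.** The point holds in a limited form. Area is measured at both ends of the study in evaluable subjects who complete it, and the plan makes no between-arm comparison of the graded change. At 73.3% v 20% the planned test has 48% power. A permutation rank test on percentage change has about 58% to 84%, with the upper end resting on similar SDs in the two arms. It beat Fisher in every case run at those rates, but not at low control rates with a much larger laser-arm SD. All rank-test figures rest on the assumed distribution in step 4, and the Fisher figures on one BCC per subject.

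This is a worthwhile improvement to the plan and does not invalidate the primary analysis. Power for CR+PR is unchanged by it.

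**What to change.** Keep CR+PR as the primary endpoint. In Section 13.3.2, replace the sentence "We also report percentage change in lesion size for both treatment and control arms" with a pre-specified supportive comparison:
- **Measure:** percentage change from baseline to Day 84 in total lesion area per subject, summed over lesions if there are several.
- **Test:** exact one-sided permutation rank test on subjects. At 15 v 5 there are only 15,504 allocations, so all can be enumerated.
- **Estimate:** Hodges-Lehmann difference between arms with a two-sided 95% interval.
- **Cleared lesions:** enter as zero area, so a fully cleared subject scores -100%.
- **Subjects withdrawn for progression:** enter with the worst rank or the last measured area, with one rule chosen in advance. If worst rank is used for the test, say which value enters the Hodges-Lehmann estimate.

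Do not make untransformed or log-area ANCOVA the key analysis, since it can lose power against Fisher when SDs differ or areas are zero. State no power figure for the new comparison unless its assumed SDs are given.

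The cost is plan wording and a few lines of code, with no new data, visits or subjects. The downside is one more analysis, labelled supportive, that rests on unblinded clinical measurement and does not replace histology.
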